DSMB	Data and Safety Monitoring Board
eCRF	Electronic Case Report Form
EDC	Electronic Data Capture
ERC	Ethics Review Committee
FDA	Food and Drug Administration
FTND	Fagerström Test for Nicotine Dependence
FWA	Federal Wide Assurance
GCP	Good Clinical Practice
HAM-D	Hamilton Depression Scale
HBsAB	Hepatitis B surface antibody
HBsAG	Hepatitis B surface antigen
HCV	Hepatitis C Virus
HIPAA	Health Insurance Portability and Accountability Act
HIV	Human Immunodeficiency Virus
HR	Heart Rate
IND	Investigational New Drug
IRB	Institutional Review Board
IM	Intramuscular
IV	Intravenous
LFTs	Liver Function Tests (AST, ALT, albumin and bilirubin)
LI	Lead Investigator
MD	Medical Doctor
MDMA	Methylenedioxymethamphetamine (Ecstasy)
MedDRA	The Medical Dictionary for Regulatory Activities
Mg	Milligrams

LIST OF ABBREVIATIONS (cont.)

Abbreviation	Definition
MM	Medical Management
MOP	Manual of Operations
NDA	New Drug Application
NIAAA	National Institute on Alcohol Abuse and Alcoholism
NIDA	National Institute on Drug Abuse
NIH	National Institutes of Health
NMS	Non-Study Medical and Other Services
NP	Nurse Practitioner
NTX	Naltrexone
NX	Naloxone
OHRP	Office for Human Research Protections
PA	Physician Assistant
PI	Principal Investigator
PLG	Poly lactide-co-glycolide
QA	Quality Assurance
RAB	Risk Assessment Battery
RAP-C	Research Advisory Panel of California
RRTC	Regional Research and Training Center
SAE	Serious Adverse Event
SC	Subcutaneous
SOWS	Subjective Opiate Withdrawal Scale
TAU	Treatment as Usual
TLFB	Timeline Follow-Back
UDS	Urine Drug Screen
VA	Veterans Administration
VAS	Visual Analog Scale
XR-NTX	Extended-Release Naltrexone (Vivitrol®)

1.0 INTRODUCTION

1.1 Study Objective

The primary goal of the study is to estimate the difference, if one exists, between XR-NTX and BUP-NX in the distribution of the time to relapse (i.e., loss of persistent abstinence) during the 6-month trial. Secondary objectives are to: (1) compare outcome on XR-NTX versus BUP-NX across a range of clinical safety and secondary efficacy domains, (2) explore demographic, clinical, and genetic predictors of successful treatment and moderators of differential effectiveness (i.e., what variables may help clinicians choose which of these treatments is best for a given patient), and (3) collect a limited dataset to permit analyses of economic costs and benefits of the two treatments.

1.2 Study Design

This is a multi-center, two-arm, 6-month (24-week), parallel-group, open-label, randomized controlled trial to examine the comparative effectiveness and safety of XR-NTX versus BUP-NX. Candidates will be individuals seeking treatment for opioid dependence (heroin or prescription opioids) who are admitted to an inpatient (detoxification and/or short term residential treatment) program for treatment of substance dependence. The study will be conducted in approximately 8 CTPs that: (a) provide opioid detoxification services (inpatient/residential), (b) have the capacity to maintain participants opioid-free, (c) have the capacity to initiate patients onto XR-NTX or BUP-NX, (d) have the capacity to maintain participants on XR-NTX or BUP-NX for the duration of the 24-week trial, (e) have a sufficient flow of patients completing detoxification and who do not routinely receive long-term medication-assisted therapy as to provide a sufficient population of potential participants to achieve study enrollment goals, and (f) can provide a minimum level of outpatient care (at least one group and/or individual counseling session per week) for 24 weeks. Candidates will be consented, screened, and randomized at the time of admission, during detoxification or during early abstinence. Participants meeting all eligibility criteria will be randomized to one of two treatment conditions, XR-NTX or BUP-NX. Treatment will be for 24 weeks in the context of a protocol-directed medical management treatment program and individual or group psychosocial counseling. Research visits will occur weekly for collection of urine samples and safety and other assessments. XR-NTX will be administered by injection on an approximately every-four-week basis; BUP-NX will be provided for take-home, initially on a weekly basis, transitioning to an every-two-week and then to an every-four-week schedule. Medical management for both conditions will be on a similar (weekly, transitioning to every-two-weeks, to every-four-weeks) schedule. The primary outcome measure will be the time to the event of relapse. XR-NTX will be provided as Vivitrol®. BUP-NX will be provided as Suboxone® film.

The Protocol will proceed in four phases.

Phase 1: Informed Consent, Screening, and Randomization (Days -15 through Day 0): This phase begins with informed consent during the index admission, and initiates enrollment, the conduct of all study-specific procedures and the collection of study data. During the first several days of an index admission, clinical and/or research staff will provide information about the study to potential participants (for scheduled admissions this information may be provided in advance of the admission). Guidelines for opioid detoxification are provided in the study MOP; data on detoxification utilization will be collected. This phase may take place from 1 day to 15 days. Following final review and confirmation of all eligibility criteria, randomization may proceed. Randomization may take place on the same day as informed consent and screening if recent liver function results are available, but in most cases will likely take place 2 or 3 days

later. Regardless of when randomization takes place, the date of randomization will be defined as “Day 0”.

Phase 2: Induction (Day 0 through Day 156): Following randomization, participants will be inducted onto their assigned active medication condition and treated as outpatients for 24 weeks per protocol. Guidelines for induction onto XR-NTX and onto BUP-NX are provided in the study MOP. Following induction, XR-NTX will be administered by injection approximately every 4 weeks; and BUP-NX will be quickly titrated upwards to maintenance doses. Induction should occur as soon as practicable following randomization, but may occur as late as week 22. Participants will continue into Phases 3 and 4 for research visits, even if not yet inducted onto their assigned medication.

Phase 3: Active Treatment (Week 1 through Week 24): Following randomization, participants will be inducted as soon as practicable and treated per their assigned active medication condition and followed as outpatients until 24 weeks post-randomization. Assessment visits will occur weekly. Participants whose induction onto their assigned study medication is delayed will also attend weekly research visits. Medical management visits will initially occur weekly, transition to every two weeks and then to every four weeks. In order to retain participants in treatment, and consistent with good practice, we permit flexibility with dosing. The window for Visit 1 is -3/+6 days to accommodate induction; however, induction may occur after Visit 1. A +/- 3-day window will be permissible for subsequent weekly visits. For participants who relapse and/or become lost to follow up, a -3/+28 day window is permissible to complete the EOT visit. Participants who relapse will discontinue study medication and weekly research visits, but should be encouraged to attend the week 24 and follow up visits at weeks 28 and 36.

Phase 4: Post Treatment Follow-up (Week 25 through Week 36): Toward the end of the 24-week treatment period, participants will be referred for follow-up care in the community (which could include continuation of medication, if available, indicated, and desired), and follow-up outcomes will be assessed at week 28 and week 36 post-randomization. For participants receiving BUP-NX, who do not wish to continue, or for whom community resources are not available, the study will provide a two-week BUP-NX taper (beginning at the week 24 visit). A -3/+28 day window will be permissible for the scheduled week 28 visit and a +/- 4 week window will be permissible for the scheduled week 36 visit.

1.3 Treatment Initiation

To maximize generalizability, this study has been designed to permit entry of participants throughout opioid detoxification and early abstinence. While XR-NTX can only be administered to individuals who have completed detoxification, the percentage of participants who are randomized early that are able to successfully initiate antagonist therapy is unknown. A risk to this study plan is that a differentially large percentage of individuals may be unable to initiate XR-NTX versus buprenorphine therapy.

1.3.1 Study Data Analysis Modification

Timing of the randomization is important to execution of the design and may also be an important prognostic variable. All cases are classified into one of three groups at the time of randomization, those:

- (a) randomized within 24 hours of last (licit or illicit) opioid use;
- (b) randomized between 24 and 72 hours following last (licit or illicit) opioid use;
- (c) randomized more than 72 hours following last (licit or illicit) opioid use.

Each of these groups represents different clinical scenarios commonly encountered in CTN CTPs. Group (a) represents early decision-making, at such a time as to avoid unnecessary detoxification for those choosing BUP-NX. For group (b), decision-making occurs later during

detoxification, but while participants still need to surmount the detoxification hurdle to begin XR-NTX. Group (c) includes participants who can be readily inducted onto either medication.

Individuals in groups (a) and (b) comprise the early randomizers. A data analysis modification (assessment of whether the early vs. late randomizers have a differential treatment effect and if so, time to relapse will be estimated for early and late randomizers separately) will occur if differential treatment initiation is a problem for early randomizers (i.e., significantly fewer early randomizers are able to complete detoxification and XR-NTX induction. This assessment will occur after the entry of 100 cases randomized early in the detoxification process.

1.4 Database Sources

Completed forms and electronic data will be entered into the data management system in accordance with the CRF Completion Guidelines established by the DSC. Only authorized individuals shall have access to electronic CRFs.

1.5 Randomization

Immediately following the final assessment of eligibility, participants will be randomly assigned to one of the two conditions: XR-NTX or BUP-NX. Random assignment will be on a 1:1 ratio to one of the two conditions. A restricted randomization plan will be used with centralized, automated, randomized block assignments. Randomization will be stratified by two factors, site and pre-detoxification level of opioid use. While there will be important and otherwise uncharacterized differences between sites – including state and local treatment service environments, opioid misuse epidemiology, and patient-level customs regarding treatment, medications, and clinical trial participation – the level of heroin and other opioid use will likely be an important independent predictor of treatment retention and rates of negative urines as has been demonstrated in recent analysis of naltrexone opioid trials (Sullivan et al 2006; Carpenter et al 2009; Brooks et al 2010). The level of opioid use at treatment entry is a binary classification, operationally defined as 6 or more bags (or equivalent) IV heroin per day (≥ 6 bags/day) over the 7 days prior to entry into the treatment program versus less than 6 bags (or equivalent) IV heroin per day (< 6 bags/day) or other routes of administration or other opioids.

Eligible participants will be randomized in a 1:1 ratio to the BUP-NX and XR-NTX arms. The randomization process will be performed by computer at a centralized location. Randomization will be stratified by site and pre-detoxification level of opioid use [≥ 6 or more bags (or equivalent) IV heroin per day (≥ 6 bags/day) over the 7 days prior to entry into the treatment program versus less than 6 bags (or equivalent) IV heroin per day (< 6 bags/day) or other routes of administration or other opioids]. The block size chosen will be adequate to ensure approximate treatment balance. The number in each treatment group will never differ by more than a factor of $KB/2$ where B is the block size and K is the number of strata.

The randomization procedure will be conducted in a centralized process through the Clinical Trials Network (CTN) Data and Statistics Center (DSC). The DSC statistician will generate the randomization schedule using balanced blocks of varying sizes within strata to ensure lack of predictability along with relative equality of assignment across treatment groups. The DSC statistician will review randomization data on a regular basis to ensure that the scheme is being implemented according to plan. A randomization slot, once used, will not be re-allocated. Details of the randomization process are described in a separate Randomization Plan.

1.6 Study Population

Study participants will be approximately 600 treatment-seeking heroin- and/or prescription opioid-dependent volunteers, without chronic pain requiring opioid therapy, who are willing to accept “agonist-based” or “antagonist-based” therapy. Randomization will be stratified by (1)

treatment site, and (2) baseline opioid use (high level use [≥ 6 bags {or equivalent} IV heroin/day] vs. all others [i.e., < 6 bags {or equivalent} IV heroin/day and other routes of administration or other opioids]).

1.6.1 Inclusion Criteria

1. Male or female;
2. 18 years of age and older;
3. Meet DSM-5 criteria for opioid-use disorder (heroin and/or prescription opioids);
4. Have used opioids other than as specifically prescribed within thirty days prior to consent;
5. Seeking treatment for opioid dependence and willing to accept “agonist-based” or “antagonist-based” therapy;
6. In good-enough general health, as determined by the study physician on the basis of medical history, review of systems, physical exam and laboratory assessments, to permit treatment with XR-NTX or BUP-NX;
7. Able to provide written informed consent;
8. Able to speak English sufficiently to understand the study procedures and provide written informed consent to participate in the study;
9. If female of childbearing potential, be willing to practice an effective method of birth control for the duration of participation in the study.

1.6.2 Exclusion Criteria

1. Serious medical, psychiatric or substance use disorder that, in the opinion of the study physician, would make study participation hazardous to the participant or compromise study findings or would prevent the participant from completing the study. Examples include:
 - (a) Disabling or terminal medical illness (e.g., uncompensated heart failure, cirrhosis or end-stage liver disease) as assessed by medical history, review of systems, physical exam and/or laboratory assessments;
 - (b) Severe, untreated or inadequately treated mental disorder (e.g., active psychosis, uncontrolled manic-depressive illness) as assessed by history and/or clinical interview;
 - (c) Current severe alcohol, benzodiazepine, or other depressant or sedative hypnotic use likely to require a complicated medical detoxification (routine alcohol and sedative detoxifications may be included);
2. LFTs (ALT, AST) greater than 5 times upper limit of normal;
3. Suicidal or homicidal ideation that requires immediate attention;
4. Known allergy or sensitivity to buprenorphine, naloxone, naltrexone, polylactide-co-glycolide, carboxymethylcellulose, or other components of the Vivitrol[®] diluent;
5. Maintenance on methadone at doses of 30mg or greater at the time of signing consent;
6. Presence of pain of sufficient severity as to require ongoing pain management with opioids;
7. Pending legal action or other reasons that might prevent an individual from completing the study;
8. If female, currently pregnant or breastfeeding, or planning on conception;

9. Body habitus that, in the judgment of the study physician, precludes safe intramuscular injection of XR-NTX (e.g., BMI>40, excess fat tissue over the buttocks, emaciation).

2.0 OUTCOMES

2.1 Primary Outcome

The primary outcome measure will be the time to the event, with the event called relapse. By definition individuals are abstinent at the time of randomization. Relapse occurs if the participant is using any non-protocol prescribed opioids regularly starting at day 21 post-randomization or thereafter. Operationally, loss of persistent abstinence is defined as either: (a) four consecutive opioid use weeks, or (b) seven consecutive days of use by self-report. A use week is defined as any week during which a participant self-reports at least one day of use during that week, provides a urine sample positive for non-protocol opioids, or fails to provide a urine sample. Self-report of opioid (heroin or prescription opioids) and other substance use will be ascertained at each weekly study visit using the Time Line Follow-back for each day leading back to the previous visit. Urine will be collected at each study visit and tested for opioids. In the event that a participant reports no use, but their urine test indicates use, then we will regard the week as a use week. Missing urine samples will be classified as positive. The time of the event occurs at the start of the qualifying clinical event period (e.g., first of the 7 consecutive use days or start of the 4 consecutive weeks of use).

2.2 Secondary Outcomes

Table 1: Protocol Secondary Outcomes and Hypotheses	
Outcomes	Hypotheses
Proportion successfully inducted onto assigned study medication (binary: did or did not receive first dose of XR-NTX, or achieve maintenance dose of BUP-NX)	BUP-NX will produce higher rate of successful induction than XR-NTX Significance/Rationale: XR-NTX induction requires completion of detoxification, whereas BUP-NX induction only requires onset of withdrawal symptoms. Thus XR-NTX may have more dropouts after randomization but prior to XR-NTX induction.
Adverse Events related to study medications	XR-NTX and BUP-NX will produce equivalent rates of SAEs, and equivalent rates of AEs, though AE pattern will differ somewhat (e.g. injection site reactions with XR-NTX) Significance/Rationale: Careful documentation of SAEs and AEs, including overdose episodes, would be considered essential safety data, and important component of a comparative effectiveness trial.
Opioid abstinence over time while on study medication (Weekly TLFB, confirmed by urine drug screens)	XR-NTX will produce greater opioid abstinence than BUP-NX Significance/Rationale: XR-NTX produces complete blockade of opioid effects, so that during treatment with monthly injections, opioid use can be expected to be minimal. In contrast BUP-NX may not produce complete blockade, or patients may reduce or stop doses for a few days and substitute other opioids (heroin, prescription opioids).

Table 1: Protocol Secondary Outcomes and Hypotheses	
Outcomes	Hypotheses
Alcohol and other drug use, over time (TLFB and UDS)	
XR-NTX will be superior to BUP-NX in producing abstinence from alcohol and other drugs
 
Significance/Rationale: Clinical trials show XR-NTX is effective for treatment of alcohol dependence, and naltrexone has some evidence of efficacy for stimulant dependence.

Cigarette smoking (FTND, Tobacco Use Questionnaire, VAS nicotine craving)	
XR-NTX will reduce cigarette smoking compared to BUP-NX
 
Significance/Rationale: Naltrexone has been studied as a treatment for nicotine dependence, with some support from clinical trials, although inconsistent. Given high morbidity and mortality associated with nicotine dependence, a comparative advantage of one or the other of these treatments at reducing smoking would be valuable to examine.

Opioid Craving (VAS) over time	
XR-NTX will be superior to BUP-NX in reducing opioid craving
 
Significance/Rationale: Krupitsky et al (Lancet 2011) pivotal XR-NTX trial showed, surprisingly, that XR-NTX reduced craving substantially compared to placebo.

Subacute withdrawal symptoms over time (HAM-D, SOWS)	
XR-NTX will produce greater severity of subacute withdrawal symptoms than BUP-NX during the first month after randomization, but will be equivalent to BUP-NX in months 2 to 6
 
Significance/Rationale: Low-grade withdrawal-like symptoms (dubbed “naltrexone flu” by the Columbia group, and consisting typically of insomnia, fatigue, and anorexia, though not drug craving) have been observed in some patients in the 1 to 4 weeks after naltrexone initiation, resolving gradually. Further characterization of this syndrome would be important for developing treatment guidelines.

Problems related to drug abuse (ASI-Lite and EQ-5D)	
XR-NTX will be superior to BUP-NX
 
Significance/Rationale: Greater opioid and non-opioid abstinence on XR-NTX will result in fewer problems associated with active drug abuse.

Table 1: Protocol Secondary Outcomes and Hypotheses	
Outcomes	Hypotheses
HIV risk behavior over time (RAB and other HIV risk measures)	XR-NTX and BUP-NX will be equivalent Significance/Rationale: The opioid-dependent population is at high risk for HIV, both from injection drug use and from unsafe sexual practices. Effective treatment for the opioid dependence may reduce HIV risk behavior. Given the high morbidity and mortality associated with HIV, a comparative advantage of one or the other of these treatments would be valuable to examine.
Cognitive function (Trails Making Test Parts A and B, Stroop)	XR-NTX and BUP-NX will be equivalent Significance/Rationale: Some providers and policy-makers are concerned that patients maintained on BUP-NX will have opioid-agonist-related cognitive impairment.

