3.5 Software

All analyses will be performed utilizing SAS® version 9.3. All statistical tests will be conducted at the 5% Type I error rate (two-sided). When multiple tests are conducted, the chance of finding a significant difference in one of the tests, when in fact no difference exists, is greater than the stated Type I error rate. The investigators are aware of the multiple testing issues and will interpret results with caution and use confidence intervals where possible.

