5.5.7 HIV Risk Behavior as Assessed by the RAB

The sex risk scale of the RAB, which produces a score ranging from 0-28, will be considered as a continuous response variable, and treatment effect will be analyzed using mixed effects model.

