5.5.8 Cognitive Function

The Trails Making test Parts A and B and the Stroop test will be used to assess cognitive function.

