Adverse events (AEs), including serious adverse events (SAEs), will be summarized by body system and preferred term using MedDRA (The Medical Dictionary for Regulatory Activities) version 19.0 or higher. Adverse events will be presented in two ways: (1) the number and proportion of participants experiencing at least one incidence of each event will be presented overall and by treatment group. The incidence of adverse events and serious adverse events by

type will be compared between treatment arms using either Fisher's Exact mid-p-value or Chi-Square analysis as appropriate; and (2) a table displaying the total number of each event will be given overall and by treatment group. Listings of serious adverse events will be given, sorted by treatment, body system and preferred term. Detail in these listings will include severity, relationship to study drug, and action taken as available.

Treatment emergent AEs are defined as AEs occurring after participants have been inducted on study medication. Induction is defined as having had an injection if in the XR-NTX arm or having been dispensed medication if in the BUP-NX arm.

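### Four outcomes carry equivalence hypotheses, but the plan sets no margin and plans only difference-type analyses, so nothing in it can support them

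*SAP*

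**What the plan says.** Table 1 in SAP 2.2 (repeated as Table 2 in protocol 9.2) gives a hypothesis for each secondary outcome. Most are directional. Four are not:

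- Safety: "XR-NTX and BUP-NX will produce equivalent rates of SAEs, and equivalent rates of AEs", with only the pattern of AEs expected to differ.
- Subacute withdrawal: worse on XR-NTX in the first month, "but will be equivalent to BUP-NX in months 2 to 6".
- HIV risk behaviour and cognitive function, each with the same words: "XR-NTX and BUP-NX will be equivalent".

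The analyses attached to them are these:

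- SAP 3.5 sets all tests at a two-sided 5% level.
- SAP 7.4.1 says the incidence of AEs and SAEs by "type will be compared between treatment arms using either Fisher's Exact mid-p-value or Chi-Square analysis as appropriate".
- SAP 5.5.7 takes the RAB sex-risk score as continuous, and "treatment effect will be analyzed using mixed effects model".
- SAP 5.5.8 says only that "The Trails Making test Parts A and B and the Stroop test will be used to assess cognitive function". SAP 5.5.5 likewise names the HAM-D and SOWS and no test. For both, only the general mixed-model rule of SAP 5.5 and the descriptive table shells apply.

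Neither document states an equivalence margin, an equivalence test, a rule for declaring equivalence, or an expected SAE or AE rate for this trial.

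**The concern.** A test whose null is no difference can reject that null or fail to reject it. Failing to reject is not evidence that the arms are alike, because a small or noisy comparison fails to reject as readily as a truly null one. To support equivalence, the interval for the difference has to lie inside a range fixed beforehand as unimportant, and the plan fixes no such range.

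Two of the four outcomes bear on questions the trial was set up to inform. Protocol 4.1 cites the criticism that post-treatment overdose risk was not properly assessed before XR-NTX was approved for opioid dependence, and protocol 10.2 makes safety after discontinuation a goal of follow-up. Cognition is included because some providers and policy-makers worry about agonist-related impairment on BUP-NX. An equivalence statement on either would be quoted, and the plan should say what would entitle the authors to make it.

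**Working it through.** **Inputs.** Two-sided 5% level (SAP 3.5). Total N about 600 (SAP 3.3) at 1:1 (SAP 1.5), so about 300 per arm. Treatment-emergent events count inducted participants only (SAP 7.4.1), so their denominators are smaller; 200 per arm is used as an assumed illustration. Event rates are not in the documents; a range of 1% to 15% in the lower-risk arm is assumed.

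**1. The plan's nearest power figure.** SAP 3.3 gives 79% power for a 20-point difference in a binary endpoint, 100 versus 100. Base rates are not stated, so five pairs were tried (30/50, 35/55, 40/60, 45/65, 50/70). Exact Fisher power is 78.7–79.2%, so the figure reproduces; the uncorrected pooled approximation gives 81.2–82.8%. It is power to find a difference between subgroups of one arm, and says nothing about equivalence between arms.

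**2. Hypothesis against analysis.**

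| Outcome | Margin | Stated analysis |
|---|---|---|
| AE and SAE rates | none | Fisher mid-p or chi-square |
| Withdrawal, months 2–6 | none | none specific; general mixed model |
| HIV risk (RAB sex-risk score) | none | mixed-model treatment effect |
| Cognition | none | none specific; general mixed model |

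**3. Power to detect a doubling of an event rate.** The approximation is Φ{[|p₂−p₁|√n − 1.96√(2p̄(1−p̄))] / √(p₁(1−p₁)+p₂(1−p₂))}. For 5% versus 10%, n = 300: (0.866 − 0.730)/0.371 = 0.367, or 64.3%. Exact enumeration of the mid-p test gives 64.6%. Exact mid-p results:

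| True rates (assumed) | 300 per arm | 200 per arm |
|---|---|---|
| 1% vs 2% | 14% | 9% |
| 2% vs 4% | 29% | 19% |
| 3% vs 6% | 42% | 29% |
| 5% vs 10% | 65% | 47% |
| 7% vs 14% | 80% | 63% |
| 10% vs 20% | 94% | 81% |
| 15% vs 30% | 99% | 95% |

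By the approximation, power falls below 50% when the lower rate is under about 3.6% (300 per arm) or 5.3% (200 per arm).

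**4. What a null result would leave open.** If both arms of 300 show the same rate p, the upper 95% limit for the risk ratio is exp{1.96√[2(1−p)/(300p)]}: about 3.1 at 2%, 2.0 at 5% and 1.6 at 10%. For the risk difference, the half-width 1.96√[2p(1−p)/300] is 2.2, 3.5 and 4.8 points.

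**5. What an equivalence claim would need.** With the 95% CI required to lie inside ±m, a true difference of zero and 80% power, n per arm = 2p(1−p)(1.960+1.282)²/m².

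- p = 5%, m = 5 points: 0.095 × 10.51 / 0.0025, about 400.
- p = 10%, m = 5 points: 0.18 × 10.51 / 0.0025, about 757.
- p = 2%: 165 for ±5 points, but 458 for ±3.
- A ±10-point margin needs 100 at a 5% rate and 190 at 10%.

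**6. Continuous outcomes.** A doubling has no meaning for the RAB, Trails or Stroop scores. In a simple two-group comparison with 300 per arm, 80% power corresponds to (1.960+0.842)√(2/300) = 0.23 SD.

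**The case against.** The strongest reply is that the word is used loosely. The HIV row's rationale says it would be useful to know if either treatment had an advantage, which looks for a difference. The safety rationale is about documentation, protocol 12.10 presents AEs descriptively, and no sample size or success criterion rests on these hypotheses. SAP 3.5 also promises cautious reading and interval estimates where feasible. On this view the table states expectations and nothing more.

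Much of that stands, and it makes this a wording fix and not a design fault. It does not remove the mismatch. Other rows of the table use clearly directional language, so the equivalence wording reads as a distinct claim. The promise in SAP 3.5 is a caution about multiple testing, and without a margin an interval has nothing to be judged against.

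Three stronger readings are tempting and go too far:

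- *Non-significance will be reported as equivalence.* A reader might infer this, but neither document says so.
- *A doubling of risk is likely to be missed for safety in general.* This depends on a rate the documents do not give. At 10% versus 20%, power is 81% even with 200 per arm. It is false for common AEs and for SAEs at that frequency.
- *Every planned test is a difference test.* For withdrawal and cognition no specific test is named at all.

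**Conclusion.** The mismatch holds on the text alone: four equivalence hypotheses, no margin, and no analysis that could support any of them. How much it matters depends on the outcome. For uncommon safety events, as overdose or single SAE types may be, it is material: with a lower-arm rate below about 3.6% at 300 per arm, a doubling is more likely to be missed than found, and identical observed rates of 2% would still be compatible with roughly a threefold risk. For common events, power against a doubling is good. For the continuous scores the gap is one of logic, and no size can be put on it without a margin. All event rates here are assumed, as is the 200-per-arm inducted set. The primary analysis is not affected.

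**What to change.** In SAP Table 1 (and protocol Table 2), replace the equivalence wording for the four outcomes with: *no difference is expected; the difference will be estimated*. In SAP 5.5 and 7.4.1, commit to reporting each arm difference with its 95% CI, and add a sentence that a non-significant result will not be described as equivalence. This suits the trial's primary aim, which is itself estimation.

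If the sponsor wants to keep an equivalence claim for any outcome, fix a justified margin for it before database lock and make the claim only if the CI lies inside. At event rates of 5–10%, ±5 points may not be attainable with about 300 per arm (working, step 5).

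The rewording needs no new data, no change in sample size and no clinical decision; a margin would need a clinical decision. The price is that the trial gives up an unqualified conclusion that the treatments are equivalent on these outcomes.
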